## Trevo® Retriever Registry (China)

- After deploying the Retriever within the clot, visualize strut expansion and allow sufficient time for clot integration into the Retriever (approximately 5 minutes)
- If using a BGC, inflate the balloon to arrest flow
- Slowly pull the Trevo Retriever and Trevo Microcatheter back as a unit
- As the Trevo Retriever and microcatheter are being removed, begin vigorous aspiration through the guide catheter until the Trevo Retriever is removed from the subject

NOTE: Do not perform more than six (6) retrieval attempts in the same vessel. This total number applies for any combination of retrieval devices.

Immediately after each retrieval attempt with the Trevo Retriever, perform biplane angiography in order to assess the vessel patency in the neurovascular tree that is being treated. The same angiogram orientation should be used before and after the Trevo Thrombectomy procedure to assess the reperfusion status of the vessel(s).

- If reperfusion has been successful with the Trevo Retriever (recommended modified TICI score in the territory treated is  $\geq 2b$ ) the Trevo thrombectomy procedure should be stopped and no further interventions performed.
- If reperfusion has not been successful with the Trevo Retriever continue with additional retrieval attempts (up to the maximum allowed per the IFU). At any time during the procedure, adjunctive treatment (rescue therapy) may be initiated if deemed appropriate by the treating physician.

NOTE: The Trevo thrombectomy procedure should be terminated if any of the following occur:

- Neurological deterioration or alteration in function is detected leading to the suspicion of an intracranial hemorrhage.
- Evidence of intracranial hemorrhage on imaging is noted.
- The occlusion is refractory to six retrieval attempts in a single vessel.

Neurological deterioration or alteration in function leading to the suspicion of an intracranial hemorrhage will necessitate an emergent head CT or MRI scan. At the discretion of the treating physician, this evaluation may also include angiography or other diagnostic tests to determine the etiology of the clinical alteration. Management of an intracranial hemorrhage will be performed according to each institution's usual practice.

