## 14 Adverse Events

The following adverse events will be reported:

- all adverse events that occur during the procedure
- all SAEs related to the device or the procedure through Day 90
- all serious adverse events that result in death through Day 90

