### 14.2 Relationship

The Investigator must assess the relationship of the AE to the study device using the following criteria categories and definitions:

Unrelated - The AE is due to a concurrent illness or effect of another device/drug and is not related to the study device.

Related - The AE is due to the study device (possible, probable, or highly probable).

**STRYKER CONFIDENTIAL** - THIS DOCUMENT CONTAINS CONFIDENTIAL AND PROPRIETARY INFORMATION THAT IS THE PROPERTY OF STRYKER CORPORATION. NEITHER THIS DOCUMENT NOR THE INFORMATION HEREIN MAY BE REPRODUCED, USED, OR DISCLOSED TO ANY THIRD PARTY WITHOUT THE PRIOR WRITTEN CONSENT OF STRYKER CORPORATION.

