## Trevo® Retriever Registry (China)

Unknown - The temporal relationship between the AE and study device cannot be clearly determined.

The Investigator must assess the relationship of the AE to the index procedure using the following categories and definitions:

Unrelated - The AE is due to a concurrent illness or effect of a drug and is not related to the index procedure.

Related - The AE is due to the index procedure (possible, probable, or highly probable).

Unknown - The temporal relationship between the AE and index procedure cannot be clearly determined.

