## 5. Statistical Analysis

### 5.1. Primary Endpoint

Primary Endpoint is : Revascularization status at the end of the procedure.

The primary endpoint is measured using the modified TICI scale at the end of procedure.

Success of primary endpoint was defined as a modified TICI score of 2b or better at the end of procedure.

Primary endpoint will be analyzed by percentages, frequencies and the 95% confidence interval of the percentage of success. The 95% confidence interval will be calculated using Clopper-Pearson exact method.

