**Ver AA**

**Table 5: Procedural Characteristics**

	Number of Subjects (N=xxx)
IA Medication Administered at Site of Thrombus	xx.x% (xx/xxx)
Drug Type	
Lytic Used	xx.x% (xx/xxx*)
Anti-vasospasm	xx.x% (xx/xxx*)
Other	xx.x% (xx/xxx*)
Clot Location	
CA - cervical	xx.x% (xx/xxx)
CA - petrous	xx.x% (xx/xxx)
ICA - cavernous	xx.x% (xx/xxx)
ICA - supraclinoid	xx.x% (xx/xxx)
ICAT bif	xx.x% (xx/xxx)
A1	xx.x% (xx/xxx)
A2	xx.x% (xx/xxx)
MCA-M1	xx.x% (xx/xxx)
MCA-M2	xx.x% (xx/xxx)
MCA-M3	xx.x% (xx/xxx)
Vert	xx.x% (xx/xxx)
P1	xx.x% (xx/xxx)
P2	xx.x% (xx/xxx)
Target Vessel - Laterality	
Right	xx.x% (xx/xxx)
Left	xx.x% (xx/xxx)
Target Vessel Pass Basilar	
Proximal	xx.x% (xx/xxx)
Mid	xx.x% (xx/xxx)
Distal tip	xx.x% (xx/xxx)
Baseline Imaging	
CTP/CTA	xx.x% (xx/xxx)
MRI/MRA	xx.x% (xx/xxx)
Non-Contrast CT Only	xx.x% (xx/xxx)
Embolization to New Territory Observed	xx.x% (xx/xxx)
Distal Embolization Observed	xx.x% (xx/xxx)
Number Passes of Trevo® Retriever(s)	
Mean $\pm$ SD (N)	xx.x $\pm$ xx.x (xxx)

STRYKER CONFIDENTIAL - THIS DOCUMENT CONTAINS CONFIDENTIAL AND PROPRIETARY INFORMATION THAT IS THE PROPERTY OF STRYKER CORPORATION. NEITHER THIS DOCUMENT NOR THE INFORMATION HEREIN MAY BE REPRODUCED, USED, OR DISCLOSED TO ANY THIRD PARTY WITHOUT THE PRIOR WRITTEN CONSENT OF STRYKER CORPORATION

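### Protocol 14.2 lets an SAE from a drug given during the thrombectomy be coded unrelated to the procedure, so its harm can leave the related-SAE endpoint while its angiographic benefit counts in the primary endpoint

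*Protocol*

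**What the plan says.** Protocol 14.2 asks the investigator for two attributions. For the device, one category reads "Unrelated - The AE is due to a concurrent illness or effect of another device/drug and is not related to the study device". For the procedure, the matching category reads "Unrelated - The AE is due to a concurrent illness or effect of a drug and is not related to the index procedure". The opposite category is wide: "Related - The AE is due to the index procedure (possible, probable, or highly probable" and the bracket closes there, so a possible link is enough. A third category, *Unknown*, covers an unclear temporal relationship. Appendix B does not define the index procedure.

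Drugs are expected during the procedure. Protocol 8.3 states: "At any time during the procedure, adjunctive treatment (rescue therapy) may be initiated if deemed appropriate by the treating physician". SAP Table 5 has a row for "IA Medication Administered at Site of Thrombus", split into lytic, anti-vasospasm and other.

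On benefit, SAP 5.1 states: "Success of primary endpoint was defined as a modified TICI score of 2b or better at the end of procedure". Protocol 5.3 places the end of the procedure at the final cerebral angiogram, which comes after any rescue treatment.

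On harm, secondary endpoint 4 is the rate of device- and procedure-related SAEs through Day 90 (Protocol 5.2, SAP 5.2.2). After the procedure, Protocol 14 asks for "all SAEs related to the device or the procedure through Day 90", plus SAEs that result in death.

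**The concern.** A drug effect is one of only two named grounds for calling an AE unrelated to the procedure, and nothing exempts drugs that are themselves part of that procedure. The same intra-arterial drug can therefore help produce a success in the primary endpoint while a serious bleed blamed on it is left out of the safety endpoint meant to describe the same procedure.

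Two things are at stake. The first is comparability: the related-SAE rate would depend on how each of up to 15 sites divides blame between drug and procedure. The second is balance: when the drug ground is applied to a procedural drug, it can only take events out of endpoint 4. The registry's stated purposes include monitoring safety and detecting rare complications (Protocol 6), and its data may support expanded indications (Protocol 4.2), so one or two serious events matter.

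**Working it through.** The documents give no figure on this point, so the check is first one of wording and then one of scale.

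**1. The definition.** The procedure category has two conditions joined by *and*: the AE is due to a concurrent illness or a drug effect, and it is not related to the index procedure. The second condition only restates the category being defined. It helps only if the investigator already knows whether a drug given on the table belongs to the index procedure, and no text says so.

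**2. One case, two codings.** Take a subject who reaches mTICI 2b after Trevo plus intra-arterial lytic, has a serious non-fatal bleed after the procedure, and whose bleed is blamed on the lytic.

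| | Lytic read as part of the procedure | Lytic read as a drug effect |
|---|---|---|
| Device attribution | Unrelated (another drug) | Unrelated (another drug) |
| Procedure attribution | Related (possible suffices) | Unrelated |
| Primary endpoint | Success | Success |
| Secondary endpoint 4 | In the procedure-related count | Not counted |

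Both columns fit the text. Protocol 8.3, which places rescue within the procedure, favours the first. The named drug ground in 14.2 favours the second.

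**3. Is there a later check?** Protocol 2.1 reports that TREVO had a Clinical Events Committee that independently reviewed relatedness. Here the investigator decides (14.2), the core lab adjudicates images (5.3), and the Steering Committee's remit (16) covers protocol review, progress and publication. No adjudication of events is described.

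**4. Is the event collected at all?** The documents conflict:
- Related SAEs and deaths only, after the procedure: Protocol 14 and the AE footnote in Appendix D. Protocol 14.3 likewise limits required AEs to fatal and to device- and procedure-related ones.
- Any SAE: the closing lines of Protocol 8.4, 8.5, 8.6.1 and 8.6.2, although the data lists in those same sections name only related SAEs.
- All SAEs, including a block for those related to neither device nor procedure: SAP 5.3 and Table 12.

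**5. Scale, for illustration only.** Inputs from Protocol 2.1 (TREVO): intra-arterial lytic in 10% of cases; SICH 5.0% (3/60) or 8.3% (5/60), by definition used; procedure-related SAEs 8.3% (5/60; the match with the second SICH figure is a coincidence). N = 200 from SAP 4.
- Exposed to lytic: 10% × 200 = 20.
- SICH among them, if the overall TREVO rate applied: 20 × 5.0% = 1.0 to 20 × 8.3% = 1.7, so 1-2 subjects.
- Procedure-related SAE subjects: 200 × 5/60 = 16.7, about 17, or 8.5% (Clopper-Pearson 95% CI 5.0-13.3%).
- One removed: 16/200 = 8.0% (4.6-12.7%). Two removed: 15/200 = 7.5% (4.3-12.1%).

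Range under assumptions that the documents do not supply: with 5-30% procedural drug use and 5-20% serious drug harm among those exposed, the subjects whose status turns on coding run from 200 × 5% × 5% = 0.5 to 200 × 30% × 20% = 12, or 0.25 to 6 percentage points. At 10% use the range is 1-4 subjects (0.5-2.0 points). Each figure supposes that every such event is coded unrelated, so each is an upper limit for its inputs.

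**The case against.** A reader might infer that the rule automatically removes every drug-caused SAE. The text does not support that: drug causation alone does not meet the definition, and a possible link to the procedure is enough for *Related*. A bleed after thrombectomy plus lytic could readily be coded related. This stands, and it is why the point is one of permission and ambiguity.

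A reader might also infer that such an event would never be reported and could not be recovered. That does not hold either, given the any-SAE lines in Protocol 8.4 to 8.6 and the all-SAE analysis in the SAP. What holds is that the instructions contradict each other.

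Other measures do not depend on attribution: all AEs during the procedure, fatal SAEs, Day 90 mortality and mRS, and 24-hour neurological deterioration. This also stands, with limits. Deterioration requires a rise of four or more NIHSS points over baseline, and none of these measures returns a miscoded event to endpoint 4. CT/MR is scheduled at 24 hours, but no sample table in the SAP reports haemorrhage from it.

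The claim that the endpoint is always biased favourably is not shown. Counting possible links as related can over-attribute, for instance a bleed from earlier IV tPA, and *Unknown* is also available. TREVO itself shows no sign of lost events: all three of its SITS-MOST haemorrhages were attributed to device or procedure, though by a committee and under a different protocol.

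Finally, a device registry may reasonably wish to separate drug effects, and the endpoint is descriptive with no threshold. Both are fair. Separation, however, needs a stated rule and a field to record it, and the plan has neither.

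**Conclusion.** The point holds as a flaw in a definition that feeds a named secondary endpoint. Protocol 14.2 allows harm from a drug given within the procedure to be coded unrelated to both device and procedure, while the primary endpoint credits the result obtained with that drug. The benefit side is unambiguous: there is no rule for rescue, although Table 3 of the protocol notes that TREVO 2 counted intra-arterial t-PA as a failure. The harm side is left to each investigator.

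The likely size is small: about 1-2 of 200 subjects, 8.5% falling to 7.5-8.0%, well within the sampling uncertainty of 5.0-13.3%. This rests on TREVO's lytic use and SICH rates carrying over, on the overall SICH rate applying to lytic users, and on all such events being coded unrelated. Larger losses are possible only under use and harm rates that the documents do not give. A larger sample would not remove the inconsistency between sites. The gap should be closed, but it does not invalidate the registry.

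Rescue devices are a lesser matter. The procedure category does not list another device as a ground for *Unrelated*, so harm from a rescue device can already count as procedure-related.

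**What to change.** - In Protocol 14.2, define the index procedure as running from arterial puncture to the final cerebral angiogram, including the devices and drugs used in it.
- Reword the procedure category *Unrelated* to: *due to a concurrent illness, or to a drug given outside the index procedure, and not related to the index procedure*.
- Add one eCRF attribution field (Trevo / rescue device / procedural drug / IV lytic before the procedure), so that SAP Table 12 can still show Trevo-related events separately.
- Reconcile Protocol 14, 14.3 and Appendix D with the closing lines of Protocol 8.4, 8.5, 8.6.1 and 8.6.2 and with SAP 5.3 and Table 12, so that collection of an SAE does not depend on its attribution.

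The cost is a wording amendment, one extra field, and possibly a slightly less favourable procedure-related SAE rate. If the reconciliation settles on all SAEs, sites that now report only related ones will have more to enter. No rule on the clinical use of rescue treatment is proposed.

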### 14.3 Reporting Requirements

All required AEs (i.e. all AEs resulting in deaths and device and procedure related AE) will be recorded in the appropriate eCRFs.

All required SAEs and UADEs shall be reported within 24 hours of becoming aware to Stryker Neurovascular. The information can be emailed to the Stryker Neurovascular Safety Department personnel listed in Study Contacts List.

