# Trevo® Retriever Registry (China)

## Appendix D. Time and Events Schedule

Time and Events Schedule						
Assessments:	Pre-procedure (Screening /Baseline)	Procedure	24 (-6/+24) hrs post procedure	Discharge (or Day 5-7 whichever comes first)	Day 30 +14 days	Day 90*** ±14 days
Inclusion/Exclusion Criteria	✓					
Informed Consent*	✓					
Demographics and Medical History	✓					
Baseline Medications	✓					
Baseline Labs (PT, PTT platelets, INR, glucose). Pregnancy test, if applicable	✓					
mRS**	✓			✓	✓	✓
NIHSS assessment	✓		✓	✓		
Stroke onset/etiology	✓			✓		
CT/MR Y	✓		✓			
Angiogram Procedure Information ****Y		✓				
Hospital Stay/Discharge Disposition				✓		
Post Discharge Follow-up****					✓	✓
Adverse Events †		✓	✓	✓	✓	✓
Utilization/Economic measures ††				✓		✓
Study Completion						✓

\*Written IC must be obtained prior to any data entry.  
 \*\*Telephone mRS assessment is acceptable if subject not able to return to the clinic in person.  
 \*\*\*\*Study Staff should review the study requirements with the subject and arrange all follow-up visits at discharge.  
† All AE during procedure and only DR and PR SAE, death post procedure.  
†† De-identify forms and enter subject ID # prior to sending to Stryker  
Y CT/MR and Angiographic images will be de-identified with subject ID# if submitted to SNV or the core lab.

**STRYKER CONFIDENTIAL - THIS DOCUMENT CONTAINS CONFIDENTIAL AND PROPRIETARY INFORMATION THAT IS THE PROPERTY OF STRYKER CORPORATION. NEITHER THIS DOCUMENT NOR THE INFORMATION HEREIN MAY BE REPRODUCED, USED, OR DISCLOSED TO ANY THIRD PARTY WITHOUT THE PRIOR WRITTEN CONSENT OF STRYKER CORPORATION.**

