### 5.3. Additional Safety Analyses

#### Adverse Events

- All SAEs through Day 90.

All SAEs through Day 90 will be summarized by number of events, number of subjects with events and the percentages of subjects with events by the type of SAEs and by their relatedness.

- All AEs during procedure.

All AEs during procedure will be summarized by number of events, number of subjects with events and the percentages of the subjects with events by the type of AEs and by their relatedness.

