**Ver AA**

**Table 13: All AEs during procedure**

	# of events	Percentages of subjects with events* (N=xxx)
Total AEs	xx	xx.x% (xx/xxx)
Details of AEs during procedure	xx	xx.x% (xx/xxx)
...	xx	xx.x% (xx/xxx)
...	xx	xx.x% (xx/xxx)
...	xx	xx.x% (xx/xxx)
Study device and procedure related AEs		
Total	xx	xx.x% (xx/xxx)
Details of study device and procedure related SAE	xx	xx.x% (xx/xxx)
...	xx	xx.x% (xx/xxx)
...	xx	xx.x% (xx/xxx)
...	xx	xx.x% (xx/xxx)
Study device related AEs		
Total	xx	xx.x% (xx/xxx)
Details of study device related AEs	xx	xx.x% (xx/xxx)
...	xx	xx.x% (xx/xxx)
...	xx	xx.x% (xx/xxx)
...	xx	xx.x% (xx/xxx)
Procedure but not study device related AEs		
Total	xx	xx.x% (xx/xxx)
Details of procedure but not study device related AEs	xx	xx.x% (xx/xxx)
...	xx	xx.x% (xx/xxx)
...	xx	xx.x% (xx/xxx)
...	xx	xx.x% (xx/xxx)
Study device or procedure related AEs		
Total	xx	xx.x% (xx/xxx)
Details study device or procedure related AEs	xx	xx.x% (xx/xxx)
...	xx	xx.x% (xx/xxx)
...	xx	xx.x% (xx/xxx)
Not study device and not procedure related AEs		
Total	xx	xx.x% (xx/xxx)
Details of not study device and not procedure related SAEs	xx	xx.x% (xx/xxx)
...	xx	xx.x% (xx/xxx)
...	xx	xx.x% (xx/xxx)

\*: Some subjects may experience multiple events

STRYKER CONFIDENTIAL - THIS DOCUMENT CONTAINS CONFIDENTIAL AND PROPRIETARY INFORMATION THAT IS THE PROPERTY OF STRYKER CORPORATION. NEITHER THIS DOCUMENT NOR THE INFORMATION HEREIN MAY BE REPRODUCED, USED, OR DISCLOSED TO ANY THIRD PARTY WITHOUT THE PRIOR WRITTEN CONSENT OF STRYKER CORPORATION

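### Protocol 14.3 omits non-fatal procedural AEs not classed as related, which Section 14 and Appendix D require; sites following 14.3 literally would undercount the total and unrelated block of SAP Table 13

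*Protocol*

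**What the plan says.** Three places in the protocol set out which adverse events are collected.

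- Section 14 lists three groups to be reported: "all adverse events that occur during the procedure", "all SAEs related to the device or the procedure through Day 90" and "all serious adverse events that result in death through Day 90". The first group has no filter on seriousness or relatedness.
- The Appendix D footnote gives the same rule in short: "All AE during procedure and only DR and PR SAE, death post procedure". The schedule also has an adverse-event tick in the Procedure column.
- Section 14.3 governs data entry. It says that the required AEs go into the eCRF and spells these out, after 'i.e.', as "all AEs resulting in deaths and device and procedure related AE". It has no item for procedural events as such.

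The SAP is built on the broad rule. Section 5.3 states: "All AEs during procedure will be summarized by number of events", broken down by type and relatedness. Table 13 has a total row, several related blocks and a block headed "Not study device and not procedure related AEs".

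Section 14.2 has the investigator classify each event, separately for the device and for the procedure, as Unrelated, Related or Unknown. Neither document gives an order of precedence among the three collection rules.

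**The concern.** Relatedness should be an attribute recorded for each procedural event and then tabulated. Under the wording of 14.3 it becomes a condition of entry: unless an event is fatal, the investigator's causality judgement decides whether it reaches the database at all. Table 13 could then pool two collection rules, with no way to tell from the data which rule a given site had used.

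This matters because the registry's stated purpose includes monitoring safety and detecting rare complications, and its secondary objectives include safety data for subset analyses and for regulatory submissions. Events that were never entered may be hard to recover later. They would not show up as deviations either, because Appendix B confines that term to failures of informed consent.

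**Working it through.** The documents state no figure on this point, so there is nothing to reproduce. The check sets the rules side by side. In 14.3, 'device and procedure related' is read generously, as related to either.

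| Event | Section 14 and Appendix D | Section 14.3 | Where the SAP uses it |
|---|---|---|---|
| Procedural, classed as related | recorded | recorded | Table 13 total and related rows |
| Procedural, fatal, unrelated | recorded | recorded | Table 13 total and unrelated block |
| Procedural, non-fatal, unrelated | recorded | **not recorded** | Table 13 total and unrelated block |
| Procedural, non-fatal, Unknown | recorded | **not recorded** | Table 13 total; no row of its own |
| Post-procedure, related, serious | recorded to Day 90 | recorded | Table 12 and the related-SAE secondary endpoint |
| Post-procedure, related, non-serious | not recorded | recorded | no planned table |
| Post-procedure, fatal | recorded to Day 90 | recorded | Table 12 |

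The conflict that affects planned output is confined to the third and fourth rows. The sixth row is also a mismatch, since 14.3 drops both the word serious and the Day 90 limit, but it feeds no analysis: Table 12 covers serious events only and Table 13 covers procedural events only.

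**Size.** Two inputs are needed, and neither is in the documents. Both are assumptions:

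- *u* = share of procedural events that are non-fatal and not classed as related, taken as 10% to 50%.
- *s* = share of procedural events that occur at sites following 14.3 literally, taken as 25% to 100%.

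If *u* is the same at both kinds of site, the fraction of events missing from the Table 13 total is *s* × *u*:

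| | *u* = 10% | *u* = 50% |
|---|---|---|
| *s* = 25% | 0.25 × 0.10 = 2.5% | 0.25 × 0.50 = 12.5% |
| *s* = 100% | 1.00 × 0.10 = 10% | 1.00 × 0.50 = 50% |

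With *s* = 0, nothing is missing. Under the same assumption, the non-fatal part of the unrelated block loses a fraction *s* of its events, that is 25% to 100%. At *s* = 100% only fatal events can appear there.

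These are fractions of events. The percentage-of-subjects column behaves differently: a subject drops out of it only if none of that subject's procedural events is recordable under 14.3. A subject with one related and one unrelated event is still counted in the total. The loss in that column therefore cannot be derived from *s* and *u*.

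**The case against.** The strongest reply is that 14.3 is loose drafting rather than a second rule. The word 'required' plausibly points back to the list in Section 14, and the parenthesis then paraphrases that list badly. Section 14.2 asks for Unrelated and Unknown classifications without limiting them to fatal events, which fits collection without a filter. Section 14, Appendix D and the SAP all agree with one another, and a site working from any of these would record everything.

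There are also safeguards: protocol training (15.1), an initiation visit (18.1), data review with queries (10.1) and possible comparison of procedure and anesthesia records with the eCRF (11). The eCRF and its completion guidance are not among the documents, so actual capture cannot be judged. Because Related includes events that are only possibly related, few procedural events may end up unclassified as related, which would put *u* toward the low end.

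Much of this stands. It rules out the inference, which a reader might draw, that the total will be too low and will differ between sites: that happens only where a site takes 14.3 at its word. It also rules out the inference that the unrelated block would be empty, because fatal unrelated events remain required under 14.3 and sites using Section 14 would fill the rest.

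It does not remove the contradiction. The abbreviation 'i.e.' closes a list rather than illustrating it, and 14.3 is the section on reporting requirements. The nearby text offers little correction. Section 8.3, on the procedure, has no adverse-event item, and the visit sections (8.4 to 8.6) ask for related serious events and details of deaths, which may encourage a related-only habit. Several of the monitoring steps are worded as optional.

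**Conclusion.** The point holds as a minor internal inconsistency: 14.3 is wrong as written. If it is followed literally, the Table 13 total is undercounted and the unrelated block receives only fatal events from the sites concerned. The loss is 2.5% to 50% of procedural events under the assumed ranges, and zero if all sites use Section 14 or Appendix D. The documents do not support a single figure within that range.

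No endpoint is at risk. The primary endpoint is the mTICI score. Related serious events are collected under both rules, as are deaths. Day 90 mRS and 24-hour neurological deterioration come from scheduled scales. The related rows of Table 13 are also intact. A reader might infer that the broader wording of 14.3 on post-procedure related events distorts the safety results, but no planned table uses the extra non-serious events.

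**What to change.** Reword 14.3 so that it repeats or simply cites one list, the one already in Section 14 and Appendix D:

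1. every adverse event arising during the procedure, whatever its relatedness;
2. serious events related to the device or the procedure, through Day 90;
3. serious events with a fatal outcome, through Day 90.

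Use the same list in the eCRF instructions, and have SAP 5.3 and Table 13 refer to it. Table 13 would also benefit from a row, or a stated rule, for events classed as Unknown.

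The cost is one protocol sentence, a memo to sites and a few more procedural entries. No assessment is added and no endpoint changes.
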